5.3.1.3 Expected and Unexpected Adverse Event

1416 All adverse events, be they routine or serious, will be classified as either
1417 expected or unexpected. Any adverse therapeutic experience that is associated
1418 with the study therapy or procedure and is listed as such in an investigational
1419 plan, investigational brochure, protocol or informed consent is an expected
1420 event. In contrast, any adverse therapeutic experience, the specificity or severity
1421 of which is **not** consistent with the investigational plan, investigator brochure,
1422 protocol, or informed consent for the therapy is an unexpected event.

1423

5.3.2 Adverse Event Severity Grading

1425 Severity grades are assigned by the study site to indicate the severity of all adverse
1426 experiences. The SCORE Study has adapted usage of The National Cancer Institute's
1427 Common Terminology Criteria for Adverse Events (CTCAE) for application in adverse
1428 event reporting. A copy of the CTCAE system can be found on the SCORE website:
1429 (<http://www.emmes.com/>).

1430

1431 The CTCAE provides a term and a grade that closely describes the adverse event.

1432 The CTCAE grade for each adverse event should be associated with a severity
1433 category: Grade 1 (Mild), Grade 2 (Moderate), Grade 3 (Severe), Grade 4 (Life-
1434 threatening) and Grade 5 (Death). If the adverse event is not included in the CTCAE,
1435 the following general definitions should be used in determining severity:

1436

Grade 1 Mild

Transient or mild discomforts (<48 hours), no or minimal medical intervention/therapy required, hospitalization not necessary (nonprescription or single-use prescription therapy may be employed to relieve symptoms, e.g.,

1441		aspirin for simple headache, acetaminophen for post-
1442		surgical pain). Mild adverse effects are an expected
1443		consequence of the SCORE protocol used here, and
1444		standard supportive therapies (per institutional guidelines)
1445		are permitted.
1446	Grade 2 Moderate	Mild to moderate limitation in activity, some assistance
1447		may be needed; no or minimal intervention/therapy
1448		required, hospitalization possible.
1449	Grade 3 Severe	Marked limitation in activity, some assistance usually
1450		required; medical intervention/therapy required,
1451		hospitalization possible.
1452	Grade 4 Life-threatening	Extreme limitation in activity, significant assistance
1453		required; significant medical/therapy intervention
1454		required, hospitalization or hospice care probable.
1455	Grade 5 Death	Death.
1456		

5.3.3 Relation to Therapy

The *physician* acting as the Principal Investigator at each study site or his/her *physician designee* should make the determination of therapy-relatedness of an adverse experience. A therapy-related determination must be made for every adverse event, regardless of severity or event type (routine AE or SAE). A causal relationship is present if a determination is made that there is a reasonable possibility that the adverse event may have been caused by the study drug.

5.3.4 Adverse Event Reporting Requirements and Procedures for Clinical Sites to the SCORE Coordinating Center

All adverse events, deaths, infections, and hospitalizations, regardless of severity, expectedness, or potential association with the investigational drug, will be entered on the appropriate form in the AdvantageEDC.

1471 **5.3.4.1 Requirements**

1472 Clinical sites are required to enter all known adverse event data from all
1473 events into the electronic adverse event form in the AdvantageEDC.

1475 Serious adverse events are required to be entered into the AdvantageEDC
1476 within 24 hours of recognition. If all information required on the event form
1477 has not been obtained, the site should submit what is available. Additional
1478 information, as it becomes available, can be submitted at a later date.

1480 **5.3.5 Reporting Procedures**

1481 For reporting of AEs and SAEs, the Site Coordinator will:

- 1482 1. Complete an Adverse Event form (page 1) in the SCORE data entry
1483 system.
- 1484 2. If the site determines that the event is **serious**, the site will complete, in
1485 detail, the Adverse Event Summary (page 2 of the Adverse Event Form).
- 1486 3. The SCORE Medical Monitor will review the Adverse Event Summary
1487 and complete an Adverse Event Review form (page 3 of the Adverse
1488 Event form).
- 1489 4. If follow-up information is required, the SCORE DCC will contact the
1490 site.
- 1491 5. If rapid reporting is required, the SCORE DCC will prepare a MedWatch
1492 and forward copies of the completed MedWatch to the SCORE Study
1493 Chair and Co-Chair, DSMC Chair, and IND sponsor who will send the
1494 MedWatch to the FDA.

1495 **5.3.6 SCORE Adverse Event Reporting Contact**

1497 The SCORE Project Director (listed in the Data Management Handbook as well as
1498 the current MOPP) may be contacted at the SCORE DCC, The EMMES Corporation,
1499 located in Rockville, Maryland. Be sure to clearly indicate the protocol number and
1500 the location of your site when contacting the SCORE DCC. Back-up personnel and
1501 procedures are in place to assure that if the Project Director is not available, other

1502 personnel at the SCORE DCC can adequately handle requests or adverse event
1503 reporting requirements. For urgent AE requests that occur after business hours (8:30
1504 – 5:00 Eastern Time), contact:

1505 [name]
1506 SCORE Project Director
1507 The EMMES Corporation
1508 [contact]

1510 **5.4 Procedure for Reporting of Pregnancy**

1511 At the time a site Principal Investigator or Study Coordinator becomes aware that a study
1512 participant has become pregnant during the study, the Principal Investigator or Study
1513 Coordinator will prepare a report on the pregnancy to be sent to the SCORE DCC that
1514 includes the following elements:

- 1515 • Participant (mother's) coded study identifier(s);
1516 • Date of last menstrual period;
1517 • Date of enrollment;
1518 • Date(s) of fluorescein angiogram(s); and
1519 • Date of last intravitreal injection or laser treatment, if any.

1520
1521 Any pregnancy that occurs during the study should be followed until the time of delivery,
1522 miscarriage or abortion. A report with any relevant information on the condition of the
1523 fetus or infant at birth should be forwarded to the SCORE DCC, including:

- 1524 • Mother's coded study identifier(s);
1525 • Gestational age at delivery, miscarriage, or abortion;
1526 • Birth weight, gender, length, and head circumference, if available;
1527 • Apgar scores recorded after birth, if available;
1528 • Any abnormalities. Report all abnormalities as a serious adverse event.

1530 **6. Statistical Considerations**

1531 **6.1 Scientific and Regulatory Objectives**

1532 The SCORE Study's scientific and regulatory objectives are to compare the efficacy and
1533 safety of standard care with intravitreal injection(s) of triamcinolone acetonide (4 mg or 1

1534 mg) to treat macular edema associated with CRVO and BRVO. Although scientific goals
1535 parallel regulatory goals, regulatory requirements demand some divergence of scientific
1536 statistical methods from regulatory statistical methods for testing the null hypothesis of no
1537 treatment effect of triamcinolone acetonide. Section 6.2 describes the formal test to be
1538 performed for drug registration, while the remaining sections describe the scientific
1539 statistical approach. The DSMC will be responsible for monitoring the SCORE Study
1540 following the scientific plan only.

1541

1542 **6.2 Formal Regulatory Statistical Test of Efficacy**

1543 For regulatory purposes, the SCORE Study will be configured as two separate and
1544 independent clinical trials “A” and “B”, each trial to serve as confirmatory of the other. To
1545 accomplish this, clinical sites will be allocated before recruitment commences to either trial
1546 “A” or trial “B”, using a method that strives for comparable geographic patterns and
1547 distributions of enrollees per center. Within each trial, CRVO and BRVO disease areas
1548 will be pooled for analysis and three primary efficacy analyses performed after no more
1549 than one year of follow-up. A detailed description of the method of assigning sites to Trial
1550 “A” and Trial “B” is provided in the SCORE Study Manual of Procedures and Policies
1551 (MOPP). The assignment of sites to Trial “A” and Trial “B” will be made prior to
1552 recruitment of subjects. One analysis will compare 1 mg steroid versus standard care, one
1553 will compare 4 mg steroid versus standard care, and one will compare 1 mg versus 4 mg
1554 steroid. The comparison will be with respect to the primary outcome measure. The
1555 primary outcome measure indicates whether or not a study eye of a participant experiences
1556 an improvement of 15 or more letters from baseline in best-corrected ETDRS visual acuity
1557 score. The significance of the three comparisons will be obtained by Hochberg’s
1558 sequentially rejective procedure, as described in detail in the MOPP, section 6.2. The
1559 overall alpha for the A trial will be no more than 0.05, and similarly for the independent B
1560 trial (more specifically, the alpha for each of the “A” and “B” trials will be diminished from
1561 0.05 by the amount of alpha previously spent on interim scientific efficacy assessments).
1562 Within trial “A” and within trial “B”, an initial analysis of treatment effect will be carried
1563 out by logistic regression to determine whether a statistical interaction exists between
1564 disease group (BRVO and CRVO) and treatment group (standard care, 4 mg steroid, and 1

1565 mg steroid). A finding of no interaction effect will provide justification for pooling the
1566 CRVO and BRVO participants within trial "A" and trial "B" and the primary efficacy
1567 analyses for regulatory purposes, as described above, will be carried out by means of
1568 logistic regression adjusting for disease area, baseline visual acuity, and center. A
1569 statistically significant interaction effect will require separate primary efficacy analyses for
1570 CRVO and for BRVO within trial "A" and with trial "B".

1571

1572 **6.3 Scientific Statistical Approach**

1573 **6.3.1 Two Independent Clinical Trials**

1574 The SCORE Study consists of two separate independent clinical trials - one for
1575 CRVO and one for BRVO. Each of these clinical trials has its own overall Type I
1576 error (alpha) = .05.

1577

1578 **6.3.2 Three Primary Questions in Each Clinical Trial**

1579 Each of these clinical trials asks three questions. One question is the comparison of
1580 standard care to 4 mg intravitreal injection(s) of triamcinolone acetonide. A second
1581 question is the comparison of standard care to 1 mg intravitreal injection(s) of
1582 triamcinolone acetonide. The third question compares 1 mg to 4 mg intravitreal
1583 injections. Within each clinical trial, the significance of the comparisons will be
1584 obtained by Hochberg's sequentially rejective procedure using an alpha level of 0.05
1585 (see the MOPP, section 6.4).

1586 **6.3.3 Primary Efficacy Outcome Measure and Time Point**

1587 Improvement by 15 or more letters from the randomization visit visual acuity to the
1588 12-month follow-up visual acuity is the primary efficacy outcome measure. Visual
1589 acuity is to be measured using E-ETDRS visual acuity testing.

1590

1591 **6.3.3.1 Primary Efficacy Analysis Method**

1592 The three treatment comparisons (1 mg versus standard care, 4 mg versus
1593 standard care, and 1 mg versus 4 mg) will be made by means of logistic
1594 regression adjusting for baseline visual acuity, clinical site, and presence of
1595 baseline macular hemorrhage in participants with BRVO. The test statistic

1596 will be compared to the critical value of the efficacy monitoring guideline
1597 (section 6.7.2). Family-wise error will be controlled at no more than 0.05 by
1598 Hochberg's sequentially rejective method, modified for interim monitoring as
1599 specified in the MOPP.

1600

1601 The analysis will be on the basis of intent to treat (ITT), treating missing
1602 observations as missing completely at random [i.e., missing data from study
1603 participants will be dropped from the analysis and noncompliance (or
1604 treatment crossover) ignored].

1605

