1784 monitoring is 0.005, the maximum amount the DSMC can "spend" is 0.005. If the
1785 DSMC looks more often, it will "spend" less per look.

1786

1787 Formally, if t is the information fraction, $B(t)$ is the 2-sided cumulative O'Brien-
1788 Fleming-type spending function of Lan & DeMets with final value $B(1) = 0.005$, and
1789 $S(t)$ is the two-sided cumulative spending function used by SCORE, then

$$1790 S(t) = \begin{cases} B(t) & \text{for } 0 \leq t < 1 \\ 0.05 & \text{for } t = 1 \end{cases}$$

1791
1792 At each interim inspection, the three comparisons will be made using the Lan-DeMets
1793 methodology, and the results combined using Hochberg's sequentially rejective
1794 procedure as described in the MOPP, section 6.4.

1795 **6.7.3 Interim Monitoring for Futility**

1796 The DSMC will consider futility as well as safety and efficacy. One method of
1797 statistically assessing futility is to use conditional power to estimate the likelihood of
1798 statistical significance given the observed efficacy results and various possible
1799 choices for the remaining results.

1800

1801 **6.7.4 Analyses and Results Requested to be Considered Prior to** 1802 **Recommending Early Termination**

1803
1804 Before recommending early termination, the DSMC will consider:

- 1805 • internal consistency of primary and secondary results
- 1806 • internal consistency of primary and secondary results by subgroups
1807 defined by baseline characteristics (e.g. visual acuity categories, categories
1808 based on length of history of CRVO or BRVO, and time period of
1809 enrollment)
- 1810 • distribution of baseline prognostic factors among the three groups
1811 (standard care, 4 mg, 1 mg)
- 1812 • consistency of primary and secondary results across clinical centers and
1813 among centers enrolling larger numbers of patients

1814 • possible bias in assessment of primary and secondary response variables,
1815 particularly visual acuity, given the unmasked implementation of standard
1816 care versus intravitreal triamcinolone
1817 • possible impact of missing data from missed patient visits for assessment
1818 of the primary and secondary response variables
1819 • possible differences in concomitant interventions or medications.

1820 **6.7.5 Study Timeline and DSMC Data Reviews**

1821 The DSMC will meet to review study data starting in November 2004, and every 6
1822 months until 3-year follow-up is concluded on all study participants. Table 6 depicts

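### Section 6.2 promises at most 0.05 overall alpha in each of trials A and B, but a same-data interaction test chooses the primary analysis and no allowance is made for that choice

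*Combined protocol and SAP*

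**What the plan says.** Section 6.2 divides the clinical sites into trials A and B, "each trial to serve as confirmatory of the other". CRVO and BRVO are to be pooled within each trial, and three comparisons (1 mg with standard care, 4 mg with standard care, 1 mg with 4 mg) are tested by Hochberg's procedure, with the detail left to the MOPP. The "overall alpha for the A trial will be no more than 0.05, and similarly for the independent B" trial. The only deduction named is that each trial's alpha is reduced from "0.05 by the amount of alpha previously spent on interim scientific efficacy assessments". Section 6.7.2 bounds that deduction: the total alpha for interim "monitoring is 0.005, the maximum amount the DSMC can" spend is 0.005, so at least 0.045 remains.

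The same paragraph of 6.2 places a step before the comparisons. A logistic regression tests for an interaction between disease (two levels) and treatment (three levels). If none is found, the diseases are pooled. A "statistically significant interaction effect will require separate primary efficacy analyses for" CRVO and BRVO.

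On covariates, the pooled model in 6.2 adjusts for disease area, baseline acuity and center. Section 6.3.3.1 uses logistic "regression adjusting for baseline visual acuity, clinical site, and presence of" baseline macular hemorrhage in BRVO, and randomisation (4.5.3) is stratified by three disease groups: CRVO, BRVO without dense hemorrhage and BRVO with it.

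**The concern.** The interaction test and the efficacy tests use the same outcomes. When no treatment works, a significant interaction arises because at least one disease shows a large chance difference between arms. That is exactly when the plan moves to by-disease testing, where such a difference is most likely to be declared significant. Hochberg's procedure controls error inside a family of three. It does not cover a data-driven choice between one family and two.

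Section 6.2 leaves open the three things that determine the true error: the level of the pre-test, the alpha for each disease in the separate branch, and any adjustment for the choice. The limit at stake belongs to the formal registration test and is promised for A and for B individually. The scientific analysis in 6.3, where CRVO and BRVO are separate trials at 0.05 each, is not affected.

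**Working it through.** **Inputs from the documents.** Null success rates 15% (CRVO, 6.4.2) and 35% (BRVO, 6.4.3); steroid rates 30% and 53% (6.4.4.1, 6.4.4.2); 162 per arm per disease, allocated 1:1:1 (6.4.5); alpha 0.05, or 0.045 after the maximum interim spend (6.7.2).

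**Assumptions not in the documents.** Sites split evenly, so 162 / 2 = 81 eyes per arm per disease in each trial; pre-test level g of 0.01, 0.05, 0.10 or 0.15; no missing data; disease the only covariate in the main runs.

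**Reproducing the plan's figures.** The two-proportion formula n = [z(1-α/2)·√(2·p̄·(1-p̄)) + z(0.80)·√(p1(1-p1) + p2(1-p2))]² / (p2-p1)², with two-sided α = 0.025, gives 147 for CRVO as stated and 144 for BRVO (stated 147). Then 147 × 1.10 = 161.7, rounded to 162, and 3 × 162 = 486. The promised alpha is also met by the pooled branch alone: 4.3% at 0.05 and 3.9% at 0.045.

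**Procedure simulated.** 200,000 null trials. A 2-df likelihood-ratio interaction test gives p. If p ≥ g, Hochberg is applied to the three pooled logistic contrasts; otherwise to three contrasts in each disease. An error is any rejection. Ranges run from Wald to likelihood-ratio tests in the by-disease analyses.

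| Pre-test level g | α 0.05, full in each disease | α 0.05, halved | α 0.045, full in each disease | α 0.045, halved |
|---|---|---|---|---|
| 0.01 | 5.1-5.2% | 4.8-5.0% | 4.7-4.8% | 4.4-4.5% |
| 0.05 | 6.8-7.2% | 5.6-6.1% | 6.2-6.6% | 5.1-5.6% |
| 0.10 | 7.7-8.5% | 5.8-6.6% | 7.0-7.8% | 5.3-6.1% |
| 0.15 | 8.3-9.3% | 5.9-6.8% | 7.5-8.5% | 5.4-6.4% |
| Always pooled | 4.3% | | 3.9% | |

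**Where the excess comes from.** Per-trial error = g × P(false positive in the separate branch, given a significant interaction) + (1-g) × P(false positive in the pooled branch, given none). A separate normal-approximation run (2,000,000 trials, α 0.05, full alpha) gives:

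- g = 0.05: 0.05 × 0.581 + 0.95 × 0.0447 = 0.0290 + 0.0425 = 0.0715
- g = 0.10: 0.10 × 0.432 + 0.90 × 0.0446 = 0.0432 + 0.0401 = 0.0833
- g = 0.15: 0.15 × 0.351 + 0.85 × 0.0446 = 0.0527 + 0.0379 = 0.0906

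The pooled branch behaves as intended. The separate branch yields a false positive in about 58% of the trials sent to it at g = 0.05. Treating the six comparisons as one Hochberg family gives almost the same error as halving alpha.

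**Sensitivity (α 0.045, full alpha, g 0.05-0.15).**

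- 73 per cell with a conservative 0.5-corrected test: 5.9-7.0%.
- 65 or 97 per cell (40/60 split of sites): 6.0-7.6%.
- Adjusted for three acuity strata: 6.3-7.6%.
- Also adjusted for 8 assumed centers (only 12,000 trials): 6.9-8.5%.

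**Joint error.** If both A and B must succeed, the largest joint null error is 0.0928² = 0.0086.

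**The case against.** The strongest reply is that 6.2 refers to a MOPP that is not available here, and the pre-test level and branch alphas could be set there. Section 6.2 also never says that each disease gets full alpha. A 0.01 pre-test with halved alpha gives 4.8-5.0%, which meets the 0.05 limit. This stands as a condition on the size of the error. It does not rescue 6.2: the MOPP is cited there for Hochberg on three comparisons, interim spend is the only deduction named, and an even split alone still exceeds the limit at pre-test levels of 0.05 to 0.15.

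A second reply is that the practical harm is limited, and much of this stands. A and B are meant to confirm each other. Requiring the same disease, comparison and direction in both trials, the joint null error is about 0.0011-0.0015. Per trial, false superiority of steroid over standard care is 2.6-3.1%, because the total also counts dose differences and results favouring standard care. Counted per disease (pre-test 0.05, full alpha), the error is 5.8% for CRVO and 5.2% for BRVO. But 6.2 makes its promise for the trial as a whole, over all three comparisons and for A and B individually, and that promise is what fails.

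**Conclusion.** The concern holds. As written, 6.2 does not secure its own limit. With full alpha in each disease and a pre-test between 0.05 and 0.15, the per-trial error is 6.8-9.3% against 5%, or 6.2-8.5% against 4.5% after the maximum interim spend. With alpha halved it is 5.6-6.8% and 5.1-6.4%. At a 0.01 pre-test the excess is a few tenths of a point or nothing. The figures rest on an even A/B split, the planning rates as null rates, and pre-test levels the plan does not give; the sensitivity runs do not change the conclusion. The error concerns the per-trial statement: joint error stays below 1% if both trials must succeed, and the scientific analysis is untouched. It should be fixed, since the registration test carries a stated property that it lacks under customary choices.

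**What to change.** State in 6.2, and match in the MOPP, the level of the interaction test and the alpha of each branch, set by simulation so that the whole two-stage procedure meets the stated limit. For example, with a 0.05 pre-test and the same alpha in the pooled family and in each disease family, about 0.0315-0.036 holds 0.05, and about 0.027-0.032 holds 0.045 (likelihood-ratio to Wald). Alternatively, restate the overall alpha as the simulated value.

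A third option is to make the pooled analysis the only confirmatory regulatory test, with the interaction and by-disease results supportive. That meets the limit but is a real trade-off. Power per trial for at least one steroid-versus-standard-care rejection (nominal 0.05, pre-test 0.05, calibration costed at 0.0325, inside the range above):

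| Scenario | Gate as written | Calibrated gate | Pooled only |
|---|---|---|---|
| Both diseases respond | 92% | 90% | 92% |
| Only CRVO responds: rejection applying to CRVO | 55% | 50% | 29% |
| Only CRVO responds: rejection also covering BRVO | 20% | 16% | 29% |
| Only BRVO responds: rejection applying to BRVO | 57% | 51% | 45% |
| Only BRVO responds: rejection also covering CRVO | 36% | 30% | 45% |

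If pooled-only is chosen, 6.2 should say openly what it gives up when only one disease responds.

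A minor, separate improvement: replace two-level disease area in the pooled model with the three-level randomisation stratum. All of this is wording in 6.2 and the MOPP, with no patients and no new data.
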